One treatment cycle will constitute 21 days. DTIC will be administered on Day 1 of each 3-week treatment cycle. Unesbulin or placebo tablets will be administered on Days 2 and 5 of Week 1 and Days 1 and 4 of Weeks 2 and 3 of each 3-week treatment cycle (Note: the preferable duration between 2 doses of unesbulin/placebo is approximately 72 hours). Based on the results from a food effect assessment in the ongoing Phase 1b Study PTC596-ONC-007-LMS, it is recommended that unesbulin/placebo be administered with food.

All subjects will receive treatment until evidence of disease progression, unacceptable toxicity, or other withdrawal criteria are met. No crossover will be permitted.

Subjects will undergo weekly assessments throughout the study. The schedule of all study efficacy, safety, PK, and laboratory assessments is shown in Table 1, including a window for completion of the activities associated with each visit. Of note, activities designed to be completed in a single day, for example, PK sampling from before dosing to 8 hours postdose, may not be split up between the 2 days of a window.

An end-of-treatment (EOT) assessment should be performed within 30 days after the end of treatment or until recovery from or stabilization of the AE, whichever occurs latest. For subjects requiring immediate initiation of a new treatment option, the EOT visit may be completed earlier. The EOT assessments are outlined in Table 1. A safety follow-up assessment should be performed by telephone call approximately 30 days (\pm 3 days) after the EOT to assess AEs and concomitant medications. Survival follow-up (sFUP) assessments should be performed by phone every 3 months (\pm 7 days) after the EOT until the later of 184 events or 2 years after the last subject is randomized.

PK Assessment

Approximately 12 randomized subjects will participate in a PK substudy at selected sites. These subjects will be assessed for PK of unesbulin, DTIC, and AIC. The target is for approximately 7 PK evaluable subjects in the unesbulin group to complete Cycle 3.

For the DTIC/AIC PK assessment, blood samples will be collected following an intensive schedule at predose and up to 24 hours postdose on Day 1 of Cycles 1 and 3. Sparse blood samples will be collected at predose and 1.25 and 4 hours postdose (start of infusion) on Day 1 of Cycles 2 and 4.

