1.5. Assessment of Efficacy

Response assessments will be performed by radiological imaging using Response Evaluation Criteria in Solid Tumors (RECIST) 1.1 criteria every 6 weeks (\pm 7 days) until disease progression. After Cycle 8, scans are to be performed every 9 weeks. If any subject responds with a complete response (CR) or partial response (PR) at any assessment, then the subsequent confirmatory scan should be performed 4 weeks after the previous scan where the objective response was first evidenced. Assessment of response and the primary endpoint, PFS, will be assessed by an independent central review (ICR) who will be blinded to treatment assignment.

Subjects should be followed with the same imaging procedure throughout the study. Computed tomography scans or magnetic resonance imaging may be used as clinically indicated. If the

subject withdraws for reasons other than tumor progression, an EOT scan should be performed if the last scan was \geq 3 weeks earlier.

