PD	Date of PD If PD occurred within the timeframe of 2 consecutive scheduled scans ^a from the last adequate response assessment	Progressed
	Date of last adequate response assessment If the date of PD occurred after missing more than 2 consecutive scheduled scan assessments ^a	Censored
Death	Death date If death occurred within the timeframe of 2 consecutive scheduled scans ^a from the last adequate response assessment.	Progressed
	Death date If there are no post-baseline response assessments and death occurred within ≤14 weeks of the randomization date.	Progressed
	Date of randomization If there are no post-baseline response assessments and death occurred >14 weeks from the first dose.	Censored
	Date of last adequate response assessment If the date of death occurred after missing more than 2 consecutive scheduled scan assessments ^a	Censored

Table 3:	Censoring and Event Scheme for PFS
----------	------------------------------------

Abbreviations: PD, disease progression.

> 14 weeks (6+1+6+1=14) post last tumor assessment, if PD/death occurred within first 8 cycles (24 weeks) of treatment

> 17 weeks (6+1+9+1=17) post last tumor assessment, if subjects' PD/death occurs between cycle 8 and 14 (42 weeks) of treatment

> 20 weeks (9+1+9+1=20) post last tumor assessment, if subjects' PD/death occurs after cycle 14 (42 weeks) of treatment

^a 2 consecutive scheduled scan assessments are defined in weeks as follows:

The last adequate response assessment is defined as the date subject had an overall response of (CR, PR or SD or non-CR/non-PD)

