^j For subjects participating in the PK assessment, a single ECG should be taken as follows:

- Predose and 1.5, 4, and 8 hours postdose on Day 1 of Cycles 1 and 3 concurrent with intensive PK sampling for DTIC/AIC.
- Predose and 2, 4, 6, and 8 hours postdose on Day 2 of Cycles 1 and 3 concurrent with intensive PK sampling for unesbulin.

PTC596-ONC-008-LMS

Approximately 2 hours after DTIC infusion on Cycle 2.

^k Pretreatment, baseline imaging should be performed ≤14 days before Cycle 1 Day 1. On-treatment imaging should be performed every 6 weeks (±7 days). After Cycle 8, scans may be performed every 9 weeks. If any subject responds with a CR or PR at any assessment, then the subsequent confirmatory scan should be performed 4 weeks (+5 days) after the previous scan where the objective response was first evidenced. If the subject withdraws from the study for reasons other than progression of disease, EOT imaging should be performed if the last scan was ≥3 weeks earlier. Subjects should be followed with the same imaging procedure throughout the study. Computed tomography scans or magnetic resonance imaging may be used as clinically indicated.

^m Blood samples (10 mL) to assess circulating biomarkers will be collected at screening (predose) and prior to dosing on Day 1 of Cycle 3 and at the time of disease progression or EOT. Samples will be processed, stored, and shipped according to instructions in the laboratory manual. ⁿ For subjects participating in the PK assessments:

- **PK for DTIC/AIC**: On Day 1 of Cycles 1 and 3, blood samples will be collected at predose, 0.5, 1.0 (within 10 minutes before EOI), 1.25 (approximately 15 minutes post EOI), 1.5, 2, 4, 8, 10, and 24 hours postdose (SOI). On Day 1 of Cycles 2 and 4, sparse blood samples will be collected at predose, 1.25, and 4 hours postdose (SOI). If DTIC is interrupted or held in Cycle 3, then the same intensive PK sampling schedule for DTIC should be followed on the day that DTIC resumes in the subsequent cycle. For PK assessments, DTIC must be administered the day before unesbulin/placebo dosing. DTIC should not be administered on the same day as unesbulin/placebo.

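### SAP Table 3 chooses the missed-scan limit by the date of PD or death, so a progression between weeks 41 and 42 after one missed scan can be censored while one at week 41 or 43 counts

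*SAP*

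**What the plan says.** SAP Table 3 (Section 5.1.1) counts PD as an event "If PD occurred within the timeframe of 2 consecutive scheduled scans" from the last adequate response assessment. It censors at that assessment "If the date of PD occurred after missing more than 2 consecutive scheduled scan assessments". Deaths follow the same pattern.

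Footnote a turns two scans into weeks. The gap is measured from the last tumor assessment, but the limit depends on when PD or death occurs:

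- more than "14 weeks (6+1+6+1=14) post last tumor assessment, if PD/death occurred within first 8 cycles (24 weeks) of treatment";
- more than "17 weeks (6+1+9+1=17) post last tumor assessment" if PD or death falls between Cycle 8 and Cycle 14 (week 42);
- more than 20 weeks (9+1+9+1) if PD or death comes after Cycle 14.

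The scan calendar is in SAP Appendix 1, footnote k ("On-treatment imaging should be performed every 6 weeks (±7 days") and SAP Section 1.5 ("After Cycle 8, scans are to be performed every 9 weeks"). Protocol Section 3.1 fixes the cycle length: "One treatment cycle will constitute 21 days".

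**The concern.** The number of scheduled scans a subject could have missed depends on where the gap starts, because the interval changes from 6 to 9 weeks at week 24. A limit chosen by where the gap ends will be wrong for some subjects. The 17-week limit covers one 6-week and one 9-week interval, yet it is also applied to subjects whose next two intervals are both 9 weeks.

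At stake is the event rule for the primary endpoint. The same pattern of missed scans can give an event or a censoring depending on the day PD is found, and a longer gap can turn a censored subject back into an event. SAP Section 5.3.1.4 reuses Table 3 for DOR. The PFS definition in Protocol Section 8.4.2 has no missed-scan rule that could settle the matter. None of sensitivity analyses a to d in SAP Section 5.1.2 varies the rule, so none would show its effect.

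**Working it through.** **Calendar.** With 21-day cycles, Cycle 8 ends at week 24 and Cycle 14 at week 42. Scans fall at weeks 6, 12, 18, 24, 33, 42, 51 and 60.

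**The plan's figures.** 6+1+6+1 = 14, 6+1+9+1 = 17 and 9+1+9+1 = 20. All three sums are correct.

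**The same sum, started from the last scan** (next two intervals plus one week of window for each):

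- last scan at week 12 or earlier: 6+1+6+1 = 14 weeks;
- last scan at week 18 (next scans 24 and 33): 6+1+9+1 = 17 weeks;
- last scan at week 24 or later: 9+1+9+1 = 20 weeks.

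**On-schedule PD after exactly one missed scan:**

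| Last scan | Missed | PD | Gap | Footnote limit | Footnote result | Limit from last scan |
|---|---|---|---|---|---|---|
| 6 | 12 | 18 | 12 | 14 | event | 14 |
| 12 | 18 | 24 | 12 | 14 | event | 14 |
| 18 | 24 | 33 | 15 | 17 | event | 17 |
| 24 | 33 | 42 | 18 | 17 (if week 42 is not after Cycle 14) | censored | 20 |
| 33 | 42 | 51 | 18 | 20 | event | 20 |
| 42 | 51 | 60 | 18 | 20 | event | 20 |

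Only the week-24 row fails.

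**By day.** Take the last scan at elapsed day 168. The limit is 119 days (17 weeks) up to day 294 and 140 days (20 weeks) afterwards.

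- PD on day 287 (week 41): gap 119, event.
- PD on days 288 to 294: gaps 120 to 126, censored at week 24.
- PD on days 295 to 301 (to week 43): gaps 127 to 133, event.

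**Allowing for the visit windows.** The last scan can fall on days 161 to 175 and PD on days 287 to 301, which gives 15 × 15 = 225 day pairs. For PD on day b, from 287 to 294, the footnote censors when the last scan is on day b − 120 or earlier. That is 7, 8, 9, 10, 11, 12, 13 and 14 pairs, 84 in all. If elapsed day 294 is read as Cycle 15 Day 1, its 14 pairs drop out and 70 remain. Under a 20-week limit none is censored, because the largest gap is 301 − 161 = 140 days.

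**Row text against weeks.** On-schedule PD after exactly two missed scans is always censored by the weeks:

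- 6 to 24: gap 18 > 14;
- 12 to 33: gap 21 > 17;
- 18 to 42: gap 24 > 17;
- 24 to 51: gap 27 > 20.

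The row text asks for more than two.

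**Size.** The inputs are 300 subjects randomized 2:1 (200 and 100; Protocol Section 8.2) and exponential PFS with assumed medians of 4 and 2 months, at 4.348 weeks per month. The documents give no missed-scan rate, so 3%, 5% and 10% missing week 33 are assumptions.

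- Share progressing between weeks 24 and 42, S(24) − S(42): 0.197 on unesbulin and 0.112 on control.
- Number progressing: 200 × 0.197 + 100 × 0.112 = 50.6.
- Of these, missing week 33: 1.5, 2.5 or 5.1.
- With scan days spread evenly over the windows, × 84/225 = 0.57, 0.94 or 1.89; × 70/225 = 0.47, 0.79 or 1.57.

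Other medians change little. Control at 1.5 with unesbulin at 4 gives 200 × 0.197 + 100 × 0.067 = 46.1 in place of 50.6. Control at 2.5 with unesbulin at 5 (assumed) gives 200 × 0.203 + 100 × 0.148 = 55.4.

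**The case against.** **The boundary.** A reader might infer that PD at exactly week 42, the scheduled visit, is always censored. The documents do not settle that. If scans fall on Day 1 of a cycle, the week-42 scan is Cycle 15 Day 1. Cycle 14 has then ended (14 × 21 = 294 days), so the 20-week limit applies and PD is an event. Read as elapsed time, exactly 42 weeks is not after 42 weeks, and 17 weeks applies. This objection stands for that one day. It does not rescue a PD scan taken in window a few days early, or a death, after week 41 and still within Cycle 14.

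**The count.** A reader might infer that 1.5, 2.5 or 5 progressions are lost. Those figures are upper bounds, because they treat every PD between weeks 24 and 42 among subjects missing week 33 as found on a censored day. They also ignore the 11.5% dropout, the 6-month minimum follow-up (week 42 is about 42/4.348 = 9.7 months) and the futility recommendation in SAP Section 3.5.

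**The opposite error.** A reader might also object to this case: last scan week 12, weeks 18 and 24 missed, PD at week 28. The gap of 16 is within 17, so it is an event. That agrees with the literal row text, since exactly two scans is not more than two. It shows the text and weeks pulling apart, not a separate error.

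**One missed scan or two.** Protocol Section 7.1 and the SAP appendix make 9-weekly scanning after Cycle 8 optional, while SAP Section 1.5 makes it the rule. A subject kept on 6-weekly scans would have missed weeks 30 and 36 before PD at week 42. The one-missed-scan description therefore holds on the SAP's 9-weekly calendar, which is also the calendar behind the footnote's own 9-week terms.

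**Programming is determinate.** The footnote defines the phrase in weeks, so a programmer could follow it once the boundary is settled. That is fair, but the code would then reproduce the inconsistency.

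**Conclusion.** Wrong as written, and minor. The sums are correct; the fault is that the band is chosen by the date of PD or death and not by the last adequate assessment. On the 9-weekly calendar, a subject last scanned at week 24 who misses only week 33 is censored at week 24 if PD or death falls after week 41 but within Cycle 14. The two-scan span from week 24 is 20 weeks, not 17. The threshold in the row text also disagrees with the week limits.

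The expected effect is about 0.5 to 0.6, 0.8 to 0.9 or 1.6 to 1.9 subjects at assumed miss rates of 3%, 5% or 10%. This rests on 4 v 2 month medians, exponential PFS, full follow-up of 300 subjects and evenly spread scan days; dropout and the futility stop make it smaller. Under these assumptions most affected subjects would be on unesbulin (39.4 of the 50.6 at issue). A reader might infer a material bias between arms from that. The documents do not support it: they give no missed-scan rate for either arm, and the count is too small.

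**What to change.** In footnote a, choose the limit by the nominal scheduled visit of the last adequate assessment, and go on measuring the gap from the actual assessment date:

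- 14 weeks if that visit is week 12 or earlier;
- 17 weeks if it is week 18;
- 20 weeks if it is week 24 or later.

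Using the nominal visit leaves no in-window scan without a rule. A week-23 scan done for the week-24 visit takes 20 weeks, so PD at week 42 (gap 19) counts. An unscheduled or confirmatory scan takes the most recent nominal visit.

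In the Table 3 censoring rows, change more than 2 missed scans to 2 or more, so that text and weeks agree. The week-28 case above would then be censored (gap 16 > 14), consistently with the revised text. Apply the same rule to deaths and to DOR.

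The cost is an edit to the footnote and row wording and one programming line. No new data are needed.

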5.1.2. Sensitivity Analysis for PFS

The following sensitivity analyses will be performed for the primary endpoint.

- A sensitivity analysis to determine the effect of any stratification errors during the study randomization, for example the randomization of a subject with 1 prior line of therapy, occurring in the stratum of subjects with >1 prior line.
 The primary PFS analysis described in Section 5.1.1 will be re-run with the stratification variables based on actual strata. This analysis will be performed with the mITT population redefined by the actual number of prior lines of therapy.
- b. The PFS analysis described in Section 5.1.1 will be re-run including all randomized subjects (ITT population). For this analysis, the number of prior lines of therapy will be stratified using the following levels: 1, 2-3, >3.
- c. The PFS analysis described in Section 5.1.1 will be re-run restricted the mature cohort of subjects, defined as subjects in the mITT population, who have had an opportunity to complete 6 months of follow-up (time from randomization until the data-cut date is ≥ 6months).
- d. The PFS analysis described in Section 5.1.1 will be re-run restricted to subjects who received "adequate treatment exposure", defined as subjects who received at least 50% of 2 cycles of treatment with unesbulin/placebo (ie, 6 doses), received at least 2 doses of DTIC, and had a baseline and at least 1 postbaseline response assessment using RECIST Version 1.1 criteria; or subjects who died prior to Cycle 3 Day 1 and received at least 1 dose of unesbulin.

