Laboratory tests include: (1) CBC (hemoglobin, hematocrit, mean corpuscular volume, mean corpuscular hemoglobin, mean corpuscular hemoglobin concentration), WBC count, WBC differential (may be automated or manual as per institutional standards), RBC count, lymphocytes, monocytes, neutrophils, band neutrophils (if reported), eosinophils, basophils, platelets; and (2) CMP: albumin, alkaline phosphatase, total bilirubin, bicarbonate, blood urea nitrogen, calcium, chloride, creatinine, glucose, potassium, total protein, AST, ALT, and sodium.

^h For women of childbearing potential, a serum pregnancy test should be performed at screening (with a window of 7 days) and a urine pregnancy test should be performed within 24 hours of Day 1 of Cycle 1. A urine or serum pregnancy test should be performed within 24 hours prior to dosing on Day 1 of Cycle 2 and continuing every 2 cycles beginning at Cycle 4.

ⁱ For subjects not participating in the PK assessment, a single ECG should be collected on Day 1 of the first 3 treatment cycles only, approximately 2 hours after DTIC infusion. If DTIC is interrupted, then the single ECG should be collected approximately 2 hours after DTIC infusion and recorded on an unscheduled case report form page.

^j For subjects participating in the PK assessment, a single ECG should be taken as follows:

• Predose and 1.5, 4, and 8 hours postdose on Day 1 of Cycles 1 and 3 concurrent with intensive PK sampling for DTIC/AIC.

- Predose and 2, 4, 6, and 8 hours postdose on Day 2 of Cycles 1 and 3 concurrent with intensive PK sampling for unesbulin.
- Approximately 2 hours after DTIC infusion on Cycle 2.

^k Pretreatment, baseline imaging should be performed ≤14 days before Cycle 1 Day 1. On-treatment imaging should be performed every 6 weeks (±7 days). After Cycle 8, scans may be performed every 9 weeks. If any subject responds with a CR or PR at any assessment, then the subsequent confirmatory scan should be performed 4 weeks (+5 days) after the previous scan where the objective response was first evidenced. If the subject withdraws from the study for reasons other than progression of disease, EOT imaging should be performed if the last scan was ≥3 weeks earlier. Subjects should be followed with the same imaging procedure throughout the study. Computed tomography scans or magnetic resonance imaging may be used as clinically indicated.

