1.1. Study Design

This is an international, multicenter, randomized, double-blind, placebo-controlled, Phase 2/3 study to compare the efficacy and safety of unesbulin plus dacarbazine (DTIC) versus placebo plus DTIC in subjects with unresectable or metastatic, relapsed or refractory leiomyosarcoma (LMS) who have received at least 1 prior line of systemic therapy.

Eligible subjects will be randomized 2:1 (unesbulin plus DTIC: placebo plus DTIC) to one of the following treatment groups as shown in Figure 1:

- Unesbulin plus DTIC: Unesbulin 300 mg will be administered PO twice weekly (BIW) in each 3-week treatment cycle. DTIC 1000 mg/m² will be administered IV once every 21 days (Q21D).
- **Placebo plus DTIC**: Matching placebo will be administered PO BIW in each 3-week treatment cycle. DTIC 1000 mg/m² will be administered IV Q21D.

Figure 1: Study Design

Abbreviations: AE, adverse event; BIW, twice weekly; DTIC, dacarbazine; EOT, end-of-treatment; FUP, follow-up; OS, overall survival; Q21D, once every 21 days

Note: All subjects will receive treatment until evidence of disease progression, unacceptable toxicity, or other withdrawal criteria are met. An EOT assessment will be performed within 30 days after the end of treatment or until recovery or stabilization of the AE, whichever occurs latest. For subjects requiring immediate initiation of a new treatment option, an EOT visit may be completed earlier. A safety FUP assessment should be performed by phone at

30 days (±3 days) after the EOT. Survival FUP assessments will occur by phone every 3 months (±7 days) after the EOT visit until the later of 184 events or 2 years after the last subject is randomized.

For approximately 300 subjects with 1 to 3 prior lines of treatment, randomization will be stratified as follows:

- Number of prior systemic therapies (1 or >1)
- Eastern Cooperative Oncology Group (ECOG) performance status (PS) score (0 or 1)
- Histological tumor type (uterine versus nonuterine LMS)

Forty-five subjects with at least 4 prior lines of treatment will be randomized and stratified as follows:

- ECOG PS score (0 or 1)
- Histological tumor type (uterine versus nonuterine LMS)

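### SAP 5.1.2 item d readmits early deaths only for subjects who took unesbulin, so early placebo deaths drop out and the hazard ratio is biased against unesbulin

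*SAP*

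**What the plan says.** SAP section 5.1.2 lists four sensitivity analyses for the primary endpoint. Item d repeats the PFS analysis in subjects with adequate treatment exposure, and a subject can enter by either of two routes.

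- **Route 1** covers subjects who "received at least 50% of 2 cycles of treatment with unesbulin/placebo (ie, 6 doses), received at least 2 doses of DTIC" and who also had a baseline and at least one post-baseline RECIST assessment. All of these conditions must be met, and both oral treatments are named.
- **Route 2** adds "or subjects who died prior to Cycle 3 Day 1 and received at least 1 dose of unesbulin". Only the active drug is named.

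On what control subjects take, SAP section 1.1 says "Matching placebo will be administered PO BIW in each 3-week treatment cycle", and Protocol section 3.1 says "No crossover will be permitted". Nothing elsewhere in either document extends route 2 to placebo.

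**The concern.** Route 2 exists so that subjects who die too early to meet the exposure and scan conditions are not lost from the analysis. As written it does this in one arm only. Barring misdosing, no control subject can have taken unesbulin, so an early placebo death must qualify through route 1, and without a post-baseline scan it cannot.

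The analysis set is then selected on outcome, and differently by arm: the worst control outcomes leave and the worst unesbulin outcomes stay. That raises the unesbulin-to-placebo hazard ratio whatever the true effect. An effective drug looks weaker, and a neutral one looks somewhat harmful.

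SAP section 3.5 records that the Data Monitoring Committee recommended stopping for futility. In that setting an adequate-exposure analysis may be read as showing whether too little exposure explains the result. The inclusion rule would tilt that answer.

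**Working it through.** **1. Timing of the two routes.** Oral drug is given on "Days 2 and 5 of Week 1 and Days 1 and 4 of Weeks 2 and 3 of each 3-week treatment cycle" (Protocol 3.1), which is 6 doses per cycle. The SAP's own figure reproduces: 50% × 2 cycles × 6 = 6 doses. Cycle 3 Day 1 is Day 2 × 21 + 1 = 43. On-treatment scans are every 6 weeks with a 7-day window (Schedule of Assessments, imaging footnote), so the first falls at Day 42 ± 7, that is Day 35 to 49. A subject who dies before Day 43 will usually have no post-baseline scan and so fails route 1.

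**2. Status of these deaths.** SAP Table 3 counts a death with no post-baseline assessment as a PFS event if it occurs within 14 weeks (98 days) of randomization. Every death before Day 43 meets that limit. What is dropped in the control arm is therefore events, not censored observations.

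| Death before Day 43, at least one oral dose, no post-baseline scan | Route 1 | Route 2 as written | In the analysis? |
|---|---|---|---|
| Unesbulin arm | fails | passes | yes, as an event |
| Placebo arm | fails | fails | no |

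**3. The protocol's OS assumptions.** Protocol 8.2 gives median OS of 10 and 16 months (hazard ratio 0.625), 184 events, one-sided 0.025 and about 84% power. With 2:1 allocation, power = Φ(√(184 × 2/9) × |ln 0.625| − 1.96) = Φ(6.394 × 0.470 − 1.96) = Φ(1.045) = 85.2%. That agrees with the stated figure, so these medians are used below.

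**4. Expected early deaths.** Assume a constant hazard and 30.4375 days per month; 42 days = 1.38 months.

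- Placebo: 1 − 2^(−1.38/10) = 9.1%, about 9 of 100.
- Unesbulin: 1 − 2^(−1.38/16) = 5.8%, about 12 of 200.

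The 200 and 100 are the planned 300 subjects split 2:1.

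**5. Effect on the hazard ratio.** This is a simulation with 1,500 runs per scenario: exponential PFS and OS, progression seen at scans every 42 days, and an unstratified Cox model with Efron ties. Dropout is not modelled. Every early death is taken to have had at least one oral dose and no post-baseline scan, and the other route 1 conditions are not imposed. Corrected means route 2 applies to both arms.

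| Scenario (medians in months) | Corrected HR | Literal HR | Ratio |
|---|---|---|---|
| Design: PFS 2 v 4, OS 10 v 16 | 0.504 | 0.547 | 1.08 |
| No effect: PFS 2, OS 10 in both arms | 0.996 | 1.096 | 1.10 |
| No effect: PFS 2.5, OS 16 in both arms | 1.002 | 1.066 | 1.06 |
| No effect: PFS 2.5, OS 30 in both arms (assumed) | 1.001 | 1.035 | 1.03 |

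The PFS medians lie in the protocol's planning range (1.5 to 2.5 months on placebo, more than 4 on unesbulin), with 4 months taken for the active arm in the design scenario. The 30-month OS is an assumption, used to show the effect when early deaths are rare. The literal value exceeded the corrected one in at least 95% of runs in every scenario. With progression observed continuously instead of at scans, the ratios are 1.03 to 1.08.

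**6. Is the asymmetry the cause?** If early deaths are removed from both arms, the no-effect scenario with OS of 10 months gives 0.995. The shift to 1.096 therefore comes from treating the arms differently, not from removing early deaths as such.

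**7. Check with both routes applied.** A second simulation applied both entry routes and the ±7-day scan window. It again dropped about 9 of 100 placebo subjects at a 10-month median OS. The hazard ratio moved from 1.00 to 1.10 with no effect, and from 0.53 to 0.58 under the design medians (ratio 0.58/0.53 = 1.09). As a stress case, an assumed placebo median OS of 6 months gives 1 − 2^(−1.38/6) = 14.7% early deaths, and the no-effect hazard ratio moves from 1.00 to 1.16.

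**The case against.** The strongest reply is that this is shorthand. Route 1 in the same sentence names both treatments, as do SAP sections 4.8, 4.9 and 6.1, and a programmer may read route 2 the same way. There would then be no differential exclusion and no bias. That reading is probably what was meant. But the SAP is the specification, and two programmers could build different sets from it.

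A second reply is that item d decides nothing. It carries no alpha and no boundary. SAP version 1.0 (25 July 2024) already records the futility recommendation. The primary mITT analysis and items a to c impose no exposure or scan condition. A bias against unesbulin cannot create a false positive. All of this stands and limits the importance of the point.

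A third reply is that the size is an upper bound. Six oral doses are possible by Day 18 and the second DTIC dose falls at about Day 22, so a subject who dies later but was scanned first could enter by route 1. At a 10-month median only 1 − 2^(−(22/30.4375)/10) = 4.9% die by Day 22. If only deaths before Day 22 were dropped, the no-effect hazard ratio would be about 1.05; for Day 35 it would be about 1.09. So a few early placebo deaths may get in. With scans allowed from Day 35, however, the loss in the second simulation was still about 9 of 100 and the shift still about 10%. Getting down to 1.05 would need scans well before the planned window.

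Finally, the standard error of the log hazard ratio is about 0.12, so a shift of ln 1.10 = 0.095 is less than one standard error. That is true, but this is a systematic error in a known direction, and a wider interval does not correct it.

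**Conclusion.** The point holds: item d is wrong as written. Under its literal wording, nearly all placebo deaths before the first scan are excluded while the same deaths on unesbulin are kept as events, and the hazard ratio is pushed upward. On the protocol's OS medians the rise is about 8 to 10% (1.00 to 1.10 with no effect; 0.50 to 0.55 under the design medians). It falls to about 3% if early deaths are much rarer than planned.

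These figures assume constant hazards, the planned 200 and 100 subjects, and first scans near week 6. The documents give neither the actual number of early placebo deaths nor the number randomized at the futility stop, so the realised size is unknown; the direction is not. The primary result and the interim decision are untouched. This should be corrected, but it does not threaten the trial's main conclusion.

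**What to change.** In SAP section 5.1.2 item d, replace unesbulin with unesbulin/placebo in the early-death condition, so that both arms are readmitted on the same terms. The cost is one word in the SAP and one line of code. SAP section 1 already provides for revision and for documenting deviations in the clinical study report.

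If the analysis has already been run on the literal wording, rerun it and report, by arm, how many early deaths each version excludes. State alongside the result that item d, even when corrected, selects on post-randomization exposure and is not a randomized comparison; the change removes only the difference between arms.
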